8.6.1.5 Relationship to Study Drug

The causal relationship of an AE to the study drug is categorized as definitely related, probably related, probably unrelated, definitely unrelated, and undeterminable. Of these, definitely related, possibly related, and undeterminable are considered to be related to the study drug.

Table 6 Determination of causal relationship between adverse events and study drugs

definitely related	The time sequence between drug use and the onset of the AE is reasonable; the AE stops, or rapidly decreases or improves, after discontinuation of the drug; with reuse, the AE recurs and may be markedly worse (i.e., a positive re-excitation test); the event is consistent with the type of AE known to be associated with the investigational drug for the drug under suspicion; and the influence of other confounding factors, such as the original disease, has been ruled out.
probably related	The timing of the reaction is consistent with the chronological order of administration of the drug, the reaction is consistent with the type of reaction known to occur with the study drug, and the subject's clinical status or other therapeutic modalities are likely to produce the reaction.
probably unrelated	The timing of the reaction does not correspond to the chronology of the administration of the drug, the reaction is not quite consistent with the type of reaction known to occur with the investigational drug, and the subject's clinical status or other therapeutic modalities may have produced the reaction. Possibilities related to medication administration cannot be ruled out.
definitely unrelated	The timing of the reaction does not correspond to the chronological order of administration of the drug, the reaction has a type of reaction consistent with that known for non-study drugs, the subject's clinical status or other treatment modalities may also produce the reaction, the reaction is eliminated by improvement in disease status or cessation of other treatment modalities, the reaction occurs with repeated use of other treatments, and there is a strong correlation with other risk factors.
undeterminable	The timing of the reaction is not clearly related to the chronological order in which the

	medication was administered, the reaction is similar to the type of reaction known to occur with the study medication, and other medications used at the same time may cause the same reaction without an adequate basis for judgment.
AE: Adverse Eve	ents

8.6.1.6 Criteria for Severity of Adverse Events

The severity of an AE shall be documented in accordance with NCI CTCAE v5.0. The severity of an AE that is not identified in NCI CTCAE may be assessed according to the following scale:

- Grade 1: mild; asymptomatic or mild symptoms; clinical or diagnostic observations only; intervention not indicated;
- Grade 2: Moderate; minimal, localized or non-invasive interventions; age-related limitations in instrumental activities of daily living (ADLs) (instrumental ADLs are defined as cooking, grocery or clothing shopping, using the phone, money management, etc.);
- Grade 3: Severe or medically significant, but not immediately life-threatening; hospitalization or prolonged hospitalization; disability; limitations in self-ADLs (self-ADLs refer to bathing, dressing and undressing, eating, toileting, and taking medications, rather than being bedridden);
- Grade 4: life-threatening consequences; urgent intervention indicated;
- Grade 5: death related to AE.

All AEs or other signs and symptoms that occur during the course of the study should be recorded on the AE page of the eCRF, regardless of whether it is related to the clinical trial. A record should be given for any AE in all subjects who are in the study period.

8.6.1.7 Measures Related to Investigational Drugs

- Discontinuation The study drug is permanently discontinued because of a specific AE.
- Dose Unchanged No discontinuation of study drug is required for a specific AE.
- Unknown Used only when the measure taken cannot be determined.
- Not Applicable Discontinuation of the study drug for reasons other than the specific AE,
 e.g., the study was terminated, the subject died, the study drug was discontinued before the AE occurred.
- Dose Reduction Dose reduction due to a specific AE.
- Dose Interruption Temporary interruption (suspension) (including subject-initiated interruption of dosing) of an investigational drug because of a specific AE and subsequent resumption of dosing.

8.6.1.8 Outcome of Adverse Events

The outcomes of AE can be described as follows:

- Recovered/Resolved: the "(S)AE termination date" should be noted.
- Recovering/Resolving: the event is still not fully resolved, but the subject is in the recovery phase. Follow-up visits are required.
- Not Recovered/Unresolved: the incident is ongoing.
- Recovered/Resolved with Sequelae: Only if the subject will have sequelae that will last for
 a long period of time or for life, e.g., blindness due to diabetes mellitus, hemiplegia due to
 stroke. The "(S)AE termination date" should be indicated.
- Fatal: "(S)AE termination date" should be noted. Time of death needs to be recorded when AE is fatal.
- Unknown: the AE was not known to the investigator, e.g., the subject was lost to follow-up.

If the AE outcome is rated as "Recovering/Resolving", or "Not Recovered/Unresolved", or "Unknown", the AE termination date may be temporarily withheld.

The date of termination of the AE must be recorded if the AE outcome is rated as "recovered/resolved" or "recovered/resolved with sequelae."

All AEs must be followed to determine the final outcome until the event is resolved and the investigator considers the event to be stable or irreversible.

When the subject completes the clinical study, the investigator should follow the outcome of the AE related to the study drug until the event is resolved and, in the opinion of the investigator, stabilized or irreversible.

8.6.2 Collection and reporting procedures

8.6.2.1 Adverse Event Collection and Reporting

PTE and AE collection period

Collection of PTE will begin when the subject signs informed consent and continue until the subject first receives study drug or until screening failure. For subjects who withdraw from the study prior to study drug administration, PTE will be collected until the subject withdraws from the study.

Collection of AEs will begin when the subject first receives study drug and continue until 28 ± 7 days after the last dose of study drug or until initiation of new treatment for systemic cGVHD, whichever occurs first, whether or not related to study drug, and must be collected and recorded by the investigator. Only AEs/SAEs related to study treatment were collected and recorded 28 ± 7 days after the last dose of study drug or after initiation of new systemic cGVHD treatment and were required to be followed until the event was resolved and the investigator considered the event to be stabilized or irreversible.

The end date of the PTE/AE was the date when the event was resolved and deemed stable or

irreversible by the investigator.

PTE and AE Reporting

At each study visit, the investigator will assess whether a subjective AE has occurred. A neutral question may be asked, such as "How have you felt since your last visit?" . Subjects may report AEs that occur at any other time during the study.

All PTEs occurring in subjects must be monitored until symptoms subside or until any clinically relevant changes in laboratory tests have returned to baseline, or until a satisfactory explanation for the change has been provided. Non-severe PTEs related or unrelated to study operations are not required to be followed up for study protocol purposes.

All subjects experiencing AEs, whether or not related to study drug use, must be monitored until symptoms have subsided and any clinically relevant changes in laboratory test values have returned to baseline, or until a satisfactory explanation for the observed changes has been provided.

All clinically significant laboratory test abnormalities confirmed by laboratory retesting will be followed until these abnormalities have returned to acceptable levels or have been satisfactorily explained.

All PTEs and AEs that occur within the collection timeframe specified in this protocol must be fully documented on the PTE/AE page of the eCRF. The documentation must be supported by primary sources and should provide a detailed description of each incident, including the information listed below:

- Event terminology
- Start and end dates
- Severity
- Investigator's judgment of causal relationship (relevant or irrelevant) between the event and study drug administration (not required for PTE)
- Investigator's judgment of causal relationship between the event and study procedures, including details of suspected procedures
- Relevant measures taken with respect to the study drug (not applicable for PTEs)
- Event outcome

Subject diaries and questionnaires will not be used as the primary means of collecting AEs. However, if the investigator identifies a potential AE through the information collected in these documents, the subject should be followed up appropriately for medical evaluation. Through this follow-up, if it is determined that a previously unreported AE has been identified, it should be reported following normal reporting requirements.

8.6.2.2 Serious Adverse Event Collection and Reporting

For all any SAE that occurs within the collection timeframe specified in this protocol, the investigator must complete the Serious Adverse Event (SAE) Report Form provided by the sponsor or its representative, sign and date it, and report it to the sponsor and its representative by mail or fax immediately within 24 hours of being informed.

Contact Information - The fax number and e-mail address of the sponsor or his/her representative will be kept in the investigator's folder at the research center. Questions regarding drug safety and pharmacovigilance can be contacted in the above manner.

Table 7 Serious Adverse Event Reporting Units and Contact Information

Reporting unit	Fax/telephone/email
Sponsor	E-mail: [contact] ; [contact]
Representative of the sponsor	E-mail: [contact]

SAEs should detail the description of symptoms, severity, time of onset, time of management, measures taken, time and mode of follow-up and regression. All SAEs should also be completed on the eCRF form at the same time, and it needs to be ensured that the information provided on the SAE reporting form is consistent with the data recorded in the eCRF about the event.

The investigator must provide an assessment of the causal relationship of the event to the study drug at the time the SAE is reported. If the investigator is unsure whether the AE is an SAE, then it needs to be conservatively assessed as an SAE until its nature can be demonstrated.

For all SAEs, the investigator needs to follow up until there are clear results to ensure that all problems are resolved. Administer necessary treatments and therapeutic measures during follow-up to ensure that subject harm is minimized and subject safety is adequately ensured. Detailed follow-up information is recorded (e.g., at the end of the study, whether special treatment is needed, whether hospitalization is required, etc.).

The investigator is to submit a follow-up report to the sponsor until the SAE is resolved, the investigator believes the event has stabilized (returned to baseline levels, proven unresolvable/permanent), or is irreversible (death of the subject). In the case of permanent impairment, follow-up is to continue until the SAE is considered to have stabilized.

8.7 Death

8.7.1 Recording of Deaths

All deaths occurring throughout the study period (including within 28 days of the last dose of study drug, and during the survival follow-up period), including deaths resulting from disease progression, must be recorded in the appropriate module of the eCRF.

If the death of the subject occurs, the event is to be reported as an AE [if the death was due to

disease progression and the death cannot be attributed to any of the NCI CTCAE v5.0 Level 5 AEs, report the AE by disease progression with a severity level of Level 5, or, if the death of the subject was due to an AE (e.g., cardiac disease: cardiac arrest), report the death as a Level 5 for that AE], and Record the cause of death in the appropriate place on the eCRF. The investigator must determine the primary cause of death and appropriately categorize the reason for the subject's withdrawal from the trial. If the cause of death is unknown at the time of reporting, it should be recorded as "unexplained death" on the eCRF AE form and the exact cause of death should be further investigated.

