8.7.2 Reporting of death

The report of death should include information such as disease progression and primary or secondary cause of death, if any. An autopsy may be helpful in the assessment of the cause of death, and if an autopsy is performed, the report should include the results of the autopsy.

Deaths must be reported as SAEs to the sponsor or its representative within 24 hours of notification by completing the Serious Adverse Event (SAE) Reporting Form and, in accordance with GCP requirements, the investigator should provide the sponsor and the Ethics Committee with other required information such as autopsy reports and final medical reports. Deaths to be reported include the following two:

- Deaths, whether or not related to the study drug, that occurred from the time the subject signed informed consent until 28 days after the last dose of study drug;
- Deaths that are definitely related or possibly related to the study drug after 28 days after the last dose of study drug (excluding deaths that are not related to the study drug).

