5.2. Safety Endpoints

5.2.1. Adverse Events

Adverse Event

Adverse event (AE) is defined as any untoward medical occurrence in a patient administered the study medication and which does not necessarily have to have a causal relationship with the treatment.

Treatment Emergent Adverse Event

Treatment emergent adverse events (TEAE) are any AEs occurring or worsening in severity after the first administration of study medication.

Significant Adverse Event

Significant adverse events are any AEs leading to additional pertinent intervention (such as dose interruption, dose reduction or dose discontinuation).

Causality of Adverse Event

The causality with BN101/belumosudil will be classified into following 5 classes: definitely related, possibly related, unlikely related, not related, and not determined. Definitely related, possibly related, and not determined will be considered related in the analysis of related AEs.

Serious Adverse Event (SAE)

Serious adverse events (SAE) are any AE which happens during any study period (screening period, treatment period, follow up period) with any dose of the study medication and which meet one or more following criteria. Treatment emergent SAE will be summarized in the analysis.

- Result in death
- Life threatening
- Requires inpatient hospitalization or prolongation of existing hospitalization
- Result in persistent or significant disability / incapacity
- Result in a congenital anomaly / birth defect
- Other important medical events

Death

All AEs leading to death will be recorded in CRF. Death report will also be collected in CRF.

Severity of Adverse Events

Adverse event will be graded using the National Cancer Institute (NCI) Common Terminology Criteria for Adverse Events (CTCAE) version 5.0:

Grade 1: Mild; asymptomatic or mild symptoms; clinical or diagnostic observations only; intervention not indicated.

Grade 2: Moderate; minimal, local or noninvasive intervention indicated; limiting age-appropriate instrumental Activities of Daily Living (ADL) (instrumental ADL refer to preparing meals, shopping for groceries or clothes, using the telephone, managing money, etc)

Grade 3: Severe or medically significant but not immediately life-threatening; hospitalization or prolongation of hospitalization indicated; disabling; limiting self care ADL (self care ADL refer to bathing, dressing and undressing, feeding self, using the toilet, taking medications, and not bedridden)

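### Protocol 8.7.1 sets no time or relatedness limit on reporting a death as an AE, 8.6.2.1 does, and the SAP's open-ended TEAE window would count any late unrelated death so entered as a fatal TEAE

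*Protocol*

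**What the plan says.** **Recording of deaths (Protocol 8.7.1).** The first paragraph covers "All deaths occurring throughout the study period (including within 28 days of the last dose of study drug, and during the survival follow-up period" and sends them to the relevant eCRF module. The second paragraph then says: "If the death of the subject occurs, the event is to be reported as an AE". A progression death that fits no other Grade 5 term is entered as disease progression at Level 5. For a death caused by an AE, the site is to "report the death as a Level 5 for that AE". A death of unknown cause goes on the AE form as unexplained, with no grade stated. The section limits none of this by time since last dose or by relatedness.

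**AE collection (Protocol 8.6.2.1).** Collection runs from first dose to 28 ± 7 days after the last dose or "until initiation of new treatment for systemic cGVHD, whichever occurs first, whether or not related to study drug". After that, "Only AEs/SAEs related to study treatment were collected and recorded 28 ± 7 days after the last dose of study drug" or after new systemic treatment. The same section ties the AE page to this period: "All PTEs and AEs that occur within the collection timeframe specified in this protocol must be fully documented".

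**Expedited reporting of deaths (Protocol 8.7.2).** Any death up to 28 days after the last dose goes to the sponsor as an SAE. Beyond that the section names only "Deaths that are definitely related or possibly related to the study drug after 28 days after the last dose of study drug".

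**TEAE definition (SAP 5.2.1).** "Treatment emergent adverse events (TEAE) are any AEs occurring or worsening in severity after the first administration of study medication". SAP 8.5.1 tabulates fatal, serious and grade ≥3 TEAEs on that definition.

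**The concern.** An unrelated death after the AE cut-off, for example from relapse or cGVHD, is an AE on the plain wording of 8.7.1 and is outside AE collection under 8.6.2.1. Sites will learn of such deaths: Protocol 4.3.6 has subjects who stop treatment early telephoned about every 12 weeks to confirm survival. Progression and relapse are both reasons for stopping treatment (Protocol 3.3), so subjects at risk of a disease-related death are among those who enter that follow-up.

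Safety is part of the primary objective (Protocol 2), and the trial is meant to show whether safety in Chinese patients agrees with KD025-213 (Protocol 10.2; SAP 6). If late unrelated deaths enter the AE data, the fatal-TEAE rate depends partly on which section was followed and on how long subjects were followed off drug. That weakens a descriptive comparison with another trial.

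**Working it through.** The plan gives no figure on this point, so there is nothing to reproduce. The check is a comparison of the sections, followed by a simple size calculation.

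**Step 1: apply each section to four hypothetical deaths.**

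| Death | 8.7.1: AE? | 8.6.2.1: collected as AE? | 8.7.2: SAE report? |
|---|---|---|---|
| Unrelated, within 28 days and inside the AE window | Yes | Yes | Yes |
| Unrelated, more than 35 days (28 + 7) after last dose | Yes | No | No |
| Unrelated, day 20 after last dose, new systemic therapy begun on day 5 | Yes | No | Yes |
| Relationship undeterminable, more than 35 days after last dose | Yes | Yes, because 8.6.1.5 counts undeterminable as related | Not named |

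The second row is the central conflict, between 8.7.1 and 8.6.2.1. The third row shows 8.7.2 differing from 8.6.2.1, because 8.7.2 has no cut-off at new therapy. Protocol 8.6.2.2 requires the SAE form and the eCRF to agree, so a site cannot satisfy every section for that death. The fourth row shows the relatedness wording differing between 8.7.2 and 8.6.1.5.

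**Step 2: follow a late record into the SAP.** A late unrelated death entered as an AE occurs after first administration and therefore meets SAP 5.2.1. A death is serious by definition. It is grade 5 if it is a progression or AE death. No rule in SAP 5.2.1, 8.2 or 8.5.1 removes it. It reaches the fatal and serious TEAE tables and, when graded, the grade ≥3 table. It does not reach the treatment-related tables, because it is unrelated.

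**Step 3: size.** Inputs: N = 30 (Protocol 10.2), assuming that all 30 are in the Safety Set; k = number of late unrelated deaths entered under 8.7.1, not given in the documents and assumed to be 0 to 3; one death inside the AE window, also assumed.

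Shift in the fatal-TEAE rate = k/30, so each death adds 1/30 = 3.3 points. For x = 1 + k deaths, the exact (Clopper-Pearson) 95% limits are the 2.5% quantile of Beta(x, 30 − x + 1) and the 97.5% quantile of Beta(x + 1, 30 − x).

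| k | Fatal TEAEs | Rate | Exact 95% CI |
|---|---|---|---|
| 0 | 1/30 | 3.3% | 0.1 to 17.2 |
| 1 | 2/30 | 6.7% | 0.8 to 22.1 |
| 2 | 3/30 | 10.0% | 2.1 to 26.5 |
| 3 | 4/30 | 13.3% | 3.8 to 30.7 |

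The k = 0 row is also the result under 8.6.2.1, whatever the number of late unrelated deaths. For serious and grade ≥3 TEAEs the shift per death is at most 3.3 points: these tables count subjects, so a subject who already had such an event adds nothing.

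**The case against.** The best counter-reading takes the two paragraphs of 8.7.1 separately. Survival follow-up appears only in the first, which does not name the AE page; the second explains how to code a death as an AE. Several sections (7.2, 8 and 8.6.2.1 among them) end safety collection at about 28 days, and 8.6.2.1 confines the AE page to the collection period. On that reading the coding instruction sits inside the window and nothing conflicts. This is defensible, but the text does not say it. The AE instruction follows the survival follow-up sentence directly and carries no limit, so two reasonable readings give different counts.

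Other parts of the objection stand and limit the point:

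- **Every death becomes a Grade 5 AE.** A reader might infer this. Level 5 is written only for progression and AE deaths; an unexplained death has no stated grade.
- **8.7.2 is a third contradictory rule on AEs.** It governs reporting of deaths to the sponsor as SAEs and does not say that a late unrelated death stays off the AE page. It differs from 8.6.2.1 only on window and relatedness wording.
- **Fatal TEAEs would be inflated threefold.** That needs one in-window death and two late ones (1/30 against 3/30). The documents give no expected number of deaths, and with none the shift is zero.
- **Sites will in fact diverge.** One CRO data department manages data verification and queries (Protocol 9), so this is a risk, not a prediction.
- **Progression deaths should not be AEs at all.** Protocol 8.6.1.1 and 8.6.1.4 deliberately except deaths from their exclusion of progression events. Only timing is in question.

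The analyses are descriptive (SAP 6), and deaths also have their own report and listing.

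**Conclusion.** The point holds as a conflict between Protocol 8.7.1 and 8.6.2.1 that the SAP does not resolve. For an unrelated death after the AE cut-off, one section read as written calls for an AE and the other excludes it; because the TEAE window has no end, any such record counts as treatment-emergent. Each one moves the fatal-TEAE rate by 3.3 points, and the serious and grade ≥3 rates by up to 3.3 points, assuming a Safety Set of 30. For the assumed 0 to 3 deaths the fatal-TEAE shift is 0 to 10 points; the true number is unknown.

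The documents do not support any inference that deaths would be lost or that efficacy is affected. All deaths are recorded under the first paragraph of 8.7.1, so OS and the death listing are intact, and treatment-related TEAE tables do not change. It should be corrected because safety is part of the primary objective and the correction is cheap; it is no threat to the primary efficacy analysis.

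**What to change.** **Protocol**

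- In 8.7.1, enter a death as a fatal AE only if it falls within the AE collection window of 8.6.2.1 or is drug-related as defined in 8.6.1.5 (which includes undeterminable). Record all other deaths, with date and cause, in the death/survival module.
- Align 8.7.2 with this: one stated rule for deaths within 28 days of last dose but after new systemic therapy, one window, and the 8.6.1.5 definition of relatedness.

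**SAP**

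- In 5.2.1, end the TEAE window at the 8.6.2.1 cut-off, with later events counted only if drug-related. Apply this to every TEAE table in 8.5.1, including fatal, serious and grade ≥3. Changing only the fatal table would leave the other two open-ended.
- Add a table of all deaths by time from last dose (≤28 or >28 days) and cause (cGVHD progression, relapse of malignancy, other).

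**Cost.** Wording in 8.7.1 and 8.7.2, one derivation rule and one table. No new data are needed, because deaths and their causes are already recorded. Late unrelated deaths leave the TEAE tables but remain visible in the new table, the death listing and OS.
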